6.6. Concomitant Medications

Concomitant medications will be coded using GSK Drug coding dictionary, summarized, and listed. The summary of concomitant medications will show the number and percentage of subjects taking concomitant medications by Ingredient. Multi-ingredient products will be summarized by their separate ingredients rather than as a combination of ingredients. Anatomical Therapeutic Chemical (ATC) classification Level 1 (Body System) information will be included in the dataset created but will not appear on the listing or summary.

In the summary of concomitant medications, each subject is counted once within each unique ingredient. For example, if a subject takes Amoxicillin on two separate occasions, the subject is counted only once under the ingredient "Amoxicillin". In the summary of concomitant medications, the ingredients will be summarized by the base only, using CMBASECD and CMBASE. Note: In order to be considered a concomitant medication, the concomitant medication must have been taken at some point during the on-treatment window.

Prophylactic medication for infusion-related reactions and prophylactic topical eye medications will be summarized by drug class and drug name and listed separately. In addition, the percentage of duration of exposure (see Section 15.6.2 for definition) that was on prophylactic steroid eye drop use will also be summarized.

Blood products or blood supportive care products with onset date within the on-treatment window will be included in the summary tables. The frequency and percentage of subjects using blood products and blood supportive care products after the start of study medication will be provided. Supporting listings will also be provided.

6.7. Subsequent Anti-Cancer Therapies

The number and percentage of subjects that received chemotherapy, immunotherapy, hormonal therapy, biologic therapy, radioactive therapy, small molecule targeted therapy, as subsequent anti-cancer therapy will be summarized. Time from study treatment discontinuation to the first post study treatment anti-cancer therapy will also be included in this summary table, if available.

Follow-up anti-cancer therapy will be coded using GSK Drug coding dictionary, then summarized by ingredient. A listing of the type of follow-up anti-cancer therapy received (chemotherapy, immunotherapy, hormonal therapy, biologic therapy, radioactive therapy, and small molecule targeted therapy) for each subject will be provided.

7. EFFICACY ANALYSES

The efficacy analyses will be based on the ‘Intent-to-Treat’ or ‘Efficacy’ population for frozen liquid cohort alone, and ‘Full Analysis’ population for frozen liquid cohort plus lyophilized cohort (side-by-side presentation). If needed, the efficacy analyses for lyophilized cohort alone will be based on the ‘Lyo’ population.

Unless otherwise specified, no ‘Total’ column will be provided for efficacy outputs

7.1. Primary Efficacy Analyses

7.1.1. Overall Response Rate (ORR) based on IRC assessment

ORR, defined as the percentage of participants with a confirmed partial response (PR) or better (i.e., PR, very good partial response [VGPR], complete response [CR] and stringent complete response [sCR]), according to the 2016 International Myeloma Working Group (IMWG) Response Criteria [Kumar, 2016]. ORR based on Independent Review Committee (IRC) will be analyzed as the primary endpoint.

ORR at primary analysis will be analyzed based on the confirmed responses, which will be derived based on the algorithm specified in [Table 3](#).

Only the assessments from the start of treatment up to the earlier of confirmed disease progression or the start of new anti-cancer therapy will be considered. Only new systemic anti-cancer drugs taken are considered as anti-cancer therapy (radiotherapy and surgeries are not considered as systemic anti-cancer therapy for the purpose of this analysis).

Subjects with only assessments of Not Evaluable or missing response will be treated as non-responders; i.e. they will be included in the denominator when calculating the percentage.

7.1.1.1. Derivation of Confirmed Response

The derivation of confirmed response shall be based on the algorithm specified in [Table 3](#). The date of the first of the two consecutive assessments will be used as the date of the confirmed response.

Table 3 Response confirmation algorithm

#	Response at the First Time Point	Response at Subsequent Disease Assessment ¹	Confirmed Response at the First Time Point
1	sCR	sCR	sCR
2	sCR	CR	CR
3	CR	sCR/CR	
4	sCR/CR	VGPR	VGPR
5	VGPR	sCR/CR/VGPR	
6	sCR/CR/VGPR	PR	PR
7	PR	sCR/CR/VGPR/PR	
8	sCR/CR/VGPR/PR	MR	MR
9	MR	sCR/CR/VGPR/PR/MR	

#	Response at the First Time Point	Response at Subsequent Disease Assessment ¹	Confirmed Response at the First Time Point
10	sCR/CR/VGPR/PR/MR	SD	SD
11	sCR/CR/VGPR/PR/MR	PD (any reason) OR No subsequent disease assessment: subject died or discontinued study or started new anti-cancer therapy before further adequate disease assessment	NE
12	PD (due to reasons other than imaging, i.e., plasmacytoma or bone lesion)	PD (any reason) including PD after initiation of new anti-cancer therapy OR No subsequent disease assessment: subject died due to PD before further adequate disease assessment (including death due to PD after initiation of new anti-cancer therapy)	PD
13	PD (due to reasons other than imaging, i.e., plasmacytoma or bone lesion)	sCR/CR/VGPR/PR/MR/SD OR No subsequent disease assessment: subject died due to reasons other than PD before further adequate disease assessment OR No subsequent disease assessment: subject discontinued study before further adequate disease assessment	NE
14	sCR/CR/VGPR/PR/MR/PD (due to reasons other than imaging, i.e., plasmacytoma or bone lesion)	No subsequent disease assessment: subject has not died, discontinued from study or (except for PD) started new anti-cancer therapy; but as yet has no further adequate disease assessments	Unconfirmed sCR/CR/VGPR/PR/MR/PD. Will be categorized as NE for final ORR analysis. For ORR analysis in IA, the UC response (PR or better) will be counted as responder.
15	SD	Any OR No subsequent disease	SD

#	Response at the First Time Point	Response at Subsequent Disease Assessment ¹	Confirmed Response at the First Time Point
		assessment	
16	PD due to imaging (plasmacytoma or bone lesion)	Any OR No subsequent disease assessment	PD
17	NE or missing	Any OR No subsequent disease assessment	NE

1. Subsequent disease assessment is defined as the next adequate (not missing or NE) disease assessment following the first timepoint before (or on the same date of) start of new anti-cancer therapy except for confirmation of PD, for which PD or death due to PD after new anti-cancer therapy are considered for confirmation of PD. No minimal time interval is required for the subsequent disease assessment, but a different sample is required for confirmation.
2. SD does not need to be confirmed.
3. PD due to imaging (i.e., plasmacytoma or bone lesion) does not need to be confirmed.
4. Where criteria are not mutually exclusive, take the first that applies.

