7.2.1.5. Progression Free Survival (PFS)

PFS is defined as the time from randomization until the earliest date of confirmed PD per IMWG, or death due to any cause.

PFS will be analysed at the time of final ORR analysis, also at study close out if applicable, based on responses assessed by both IRC and investigator.

A summary of the assignments for progression and censoring dates for PFS are specified in [Table 4](#) below.

Table 4 Assignments for Progression and Censoring Dates for PFS Analysis

Situation	Date of Event (Progression/Death) or Censoring	Outcome Event (Progression/Death) Or Censored
No (or inadequate) baseline tumor assessments ^[1] and the subject has not died (if the subject has died follow the rules for death indicated at the bottom of the table)	Randomization	Censored
No post-baseline assessments and the subject has not died (if the subject has died follow the rules for death indicated at the bottom of the table)	Randomization	Censored
Progression documented without extended loss-to-follow-up time	Date of assessment of progression ^[1]	Event
No progression (or death)	Date of last 'adequate' assessment of response ^[2]	Censored
New anticancer treatment started (prior to documented disease progression or death) ^[3] .	Date of last 'adequate' assessment of response ^[2] (on or prior to starting anti-cancer therapy)	Censored
Death without extended loss-to-follow-up time	Date of death	Event
Death or progression after an extended loss-to-follow-up time (two or more missed cycles + 7 day window) ^[4]	Date of last 'adequate' assessment of response ^[2] prior to PD/death (prior to missed assessments)	Censored

Situation	Date of Event (Progression/Death) or Censoring	Outcome Event (Progression/Death) Or Censored
Death or progression after an extended loss-to-follow-up time from randomization	Date of randomization	Censored

[1] Adequate baseline assessment is defined as at baseline, a patient has at least one of the following measurements:
a. Serum M-protein ≥ 0.5 g/dL (≥ 5 g/L) or b. Urine M-protein ≥ 200 mg/24h or c. Serum FLC assay: Involved FLC level ≥ 10 mg/dL (≥ 100 mg/L) and an abnormal serum free light chain ratio (<0.26 or >1.65)

[2] An adequate assessment is defined as an assessment where the IRC/Investigator determined response is sCR, CR, VGPR, PR, MR, or SD.

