7.2.1.6. Time to Progression (TTP)

TTP is defined as the time from randomization until the earliest date of confirmed PD per IMWG, or death due to PD.

TTP will be analysed at the time of final ORR analysis, also at study close out if applicable, based on responses assessed by both IRC and investigator.

A summary of the assignments for progression and censoring dates for TTP are specified in Table 5.

Table 5 Assignments for Progression and Censoring Dates for TTP Analysis

Situation	Date of Event (Progression/Death) or Censoring	Outcome Event (progression/Death) Or Censored
No (or inadequate) baseline tumor assessments ^[1] and the subject has not died (if the subject has died follow the rules for death indicated at the bottom of the table)	Randomization	Censored
No post-baseline assessments and the subject has not died (if the subject has died follow the rules for death indicated at the bottom of the table)	Randomization	Censored

Situation	Date of Event (Progression/Death) or Censoring	Outcome Event (progression/Death) Or Censored
Progression documented at or between scheduled visits	Date of assessment of progression ^[1]	Event
No progression (or death)	Date of last 'adequate' assessment of response ^[2]	Censored
New anticancer treatment started (prior to documented disease progression or death) ^[3] .	Date of last 'adequate' assessment of response ^[2] (on or prior to starting anti-cancer therapy)	Censored
Death due to progression without extended loss-to-follow-up time	Date of death	Event
Death from causes other than progression without extended loss-to-follow-up time	Date of death	Censored
Death or progression after an extended loss-to-follow-up time (two or more missed cycles + 7 day window) ^[4]	Date of last 'adequate' assessment of response ^[2] prior to PD/death (prior to missed assessments)	Censored
Death or progression after an extended loss-to-follow-up time from randomization	Date of randomization	Censored

Adequate baseline assessment is defined as at baseline, a patient has at least one of the following measurements: a. Serum M-protein ≥ 0.5 g/dL (≥ 5 g/L) or b. Urine M-protein ≥ 200 mg/24h or c. Serum FLC assay: Involved FLC level ≥ 5 mg/dL (≥ 50 mg/L) and an abnormal serum free light chain ratio (<0.26 or >1.65).

An adequate assessment is defined as an assessment where the IRC/Investigator determined response is sCR, CR, VGPR, PR, MR, or SD.

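### When new therapy starts before a non-imaging PD is confirmed, event status in PFS, TTP and DoR depends on the next-line outcome, so these endpoints may be overstated

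*SAP*

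**What the plan says.** **Confirmation (SAP 7.1.1.1, Table 3 and its notes).** Imaging PD is exempt: "PD due to imaging (i.e., plasmacytoma or bone lesion) does not need to be confirmed". Any other first PD needs confirmation by the next adequate assessment on or before the start of new anti-cancer therapy. There is one exception: "except for confirmation of PD, for which PD or death due to PD after new anti-cancer therapy are considered for confirmation of PD".

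- Row 12 confirms the first PD when it is followed by "PD (any reason) including PD after initiation of new anti-cancer therapy", or by death due to PD.
- Row 13 turns it into NE after a non-PD assessment, after study discontinuation, or when "subject died due to reasons other than PD before further adequate disease assessment".
- Row 14 leaves it unconfirmed when the "subject has not died, discontinued from study or (except for PD) started new anti-cancer therapy; but as yet has no further adequate disease assessments".

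A confirmed result takes the date of the first of the two assessments.

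**Endpoints.** Section 7.2.1.5: "PFS is defined as the time from randomization until the earliest date of confirmed PD per IMWG, or death due to any cause". Section 7.2.1.6: "TTP is defined as the time from randomization until the earliest date of confirmed PD per IMWG, or death due to PD". Section 7.2.1.3 censors responders without confirmed PD by the TTP rules.

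**Censoring (Tables 4 and 5).** When new therapy comes before documented progression or death, the participant is censored at the last adequate assessment on or before that therapy, or at randomization if there is none. An adequate assessment is sCR to SD, so PD does not qualify.

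**Wording.** Section 2.2 and the rows of Tables 4 and 5 say *documented* progression. Sections 7.2.1.3, 7.2.1.5 and 7.2.1.6 say *confirmed*.

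**The concern.** Take two participants with the same first non-imaging PD, no second sample, and the same switch date. If the next regimen fails, the first PD is confirmed and is an event on its own date. If the next regimen works, the PD is never confirmed and the participant is censored before it. A treatment given outside the study decides the event status, and the censoring is tied to progression itself. That is informative censoring.

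The stake is the per-arm durability figures: median PFS, the 6-month PFS rate, TTP and DoR. They are read as absolute values within each arm, with no control arm in which an upward shift would cancel.

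**Working it through.** **Step 1: trace the rules for a first non-imaging PD in a participant who starts new therapy.**

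| What follows the first PD | Table 3 | PD status | Result if *confirmed* governs |
|---|---|---|---|
| Second PD, different sample, on or before new therapy | row 12 | confirmed | event at first PD |
| No second sample; PD or death due to PD after the switch | row 12 | confirmed | event at first PD |
| No second sample; SD or response after the switch | row 14 (note 1 does not admit that assessment) | unconfirmed | censored before first PD |
| No second sample; nothing further by cut-off | row 14 | unconfirmed | censored before first PD |
| No second sample; death from another cause, or leaves the study | row 13 | NE | censored before first PD |

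The last row holds for PFS too: the new therapy precedes the death, so the new-therapy row of Table 4 sets the earlier censoring date.

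**Step 2: direction.** On a common visit grid, let *n* be at risk at a visit, *d* have a first PD there, and *k* of those be censored at the preceding visit instead. The Kaplan-Meier step changes from d/n to (d − k)/(n − k). Since n(d − k) − d(n − k) = −k(n − d), the step is smaller whenever k > 0 and d < n, so the curve is higher.

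**Step 3: size, as an illustration only.** The SAP states no figure to reproduce.

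- From the SAP: 3-weekly assessments (15.5.4), minimum follow-up of 6 months (3.2), censoring at the last pre-PD assessment.
- Assumed: exponential time to PD with median 3 or 5 months; follow-up uniform over 6 to 12 months; every event is a PD.
- *q*, assumed 10 to 50%: share of first PDs followed by new therapy before any confirming assessment.
- *c*, assumed 0 to 100%: share of those later confirmed by PD or death due to PD, drawn at random.

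Kaplan-Meier 6-month PFS rate (200,000 simulated participants), median 3 months / median 5 months:

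| q | c = 0 | c = 30% | c = 60% | c = 90% | c = 100% |
|---|---|---|---|---|---|
| 10% | 31.5 / 50.1% | 30.4 / 49.1% | 29.3 / 48.0% | 28.3 / 46.9% | 27.9 / 46.6% |
| 25% | 37.8 / 56.0% | 34.4 / 52.9% | 31.5 / 50.0% | 28.8 / 47.4% | 27.9 / 46.6% |
| 50% | 51.7 / 67.7% | 42.8 / 60.4% | 35.5 / 53.9% | 29.6 / 48.3% | 27.9 / 46.6% |

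The c = 100% column equals counting every first PD. For c from 0 to 90% the excess, taken before rounding, runs from +0.3 to +23.7 percentage points. No cell is negative.

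**Step 4: cross-check.** If a fraction f = q(1 − c) of events is lost, the hazard falls to about (1 − f), so the rate S becomes about S^(1 − f). With median 3 months and q = 25%:

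- c = 60%: f = 0.25 × 0.40 = 0.10; 0.279^0.90 = 0.317 (simulated 0.315).
- c = 30%: f = 0.25 × 0.70 = 0.175; 0.279^0.825 = 0.349 (simulated 0.344).

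**The case against.** - **Narrow reach.** A reader might infer that every non-imaging PD followed by new therapy hangs on the next regimen. The SAP does not say that. Note 1 sets no minimum interval and asks only for a different sample, so a repeat sample on or before the first day of the new therapy settles the matter. The problem is limited to participants who switch without one. This stands.
- **The exception is not the source.** The clause in note 1 adds events that would be lost if no post-switch data counted (the c = 0 column). The overstatement comes from requiring confirmation while censoring at new therapy; the exception makes the remaining losses depend on the next-line outcome. This stands.
- **Documented against confirmed.** Read literally, Tables 4 and 5 make a PD documented before the switch an event, and nothing is lost. The endpoint definitions say confirmed, so the censoring reading is the likelier one, but it is not certain. This stands, and is itself a defect to repair.
- **Different endpoint.** Overstatement is relative to counting each first PD, and some of those might not have been reproduced. This is a reason to keep the confirmed analysis as the main one. It does not remove the dependence on the next line.
- **Size and arms.** A reader might infer a known upward bias, or a differential one between arms, for example after stopping for eye toxicity. The documents support neither. *q* and *c* are not given, the simulation ignores imaging PD and death without PD, and later follow-up can recover events. Stopping for toxicity and starting new therapy before any PD is ordinary new-therapy censoring, not this rule.
- **Already visible.** Table 2.0140 and Listing 1.0390 would let affected participants be found. The shell of Table 2.0140 has only open reason rows, though, and no analysis shows the effect.

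**Conclusion.** The point holds for participants whose first non-imaging PD has no confirming assessment on or before the start of new systemic therapy. If *confirmed* governs, their event status in PFS, TTP and DoR depends on what happens next: PD or death due to PD gives an event at the first PD, anything else gives censoring before it. Relative to counting the first PD, the three endpoints may be overstated.

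The actual size cannot be computed from the SAP. At q = 25% and a true median of 3 months, both assumed, the 6-month PFS rate would read 34.4% at c = 30% or 28.8% at c = 90%, against 27.9%. If most such PDs are later confirmed, the effect is small. ORR is not materially affected; only the split between PD and NE changes.

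**What to change.** 1. State in Tables 4 and 5 whether *documented* progression means confirmed per Table 3, and align Section 2.2.
2. Keep the IMWG-confirmed analysis as the main one. Add one pre-specified sensitivity analysis of IRC-assessed PFS, TTP and DoR: a non-imaging PD followed by new systemic anti-cancer therapy, with no intervening non-PD assessment before that therapy, is an event on the first PD date whatever happens afterwards.
3. Report the number of such participants per arm.

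Cost: one derivation flag and repeat runs of Tables 2.0060, 2.0080 and 2.0100. The sensitivity estimates may be less favourable, and they will count some PDs that a second sample might not have reproduced.

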7.1.2. Summary Measure

The number and percentage of participants with best overall response (BOR) in the following response categories will be summarized by dose level: sCR, CR, VGPR, PR, overall response (sCR+CR+VGPR+PR), minimal response (MR), stable disease (SD), progressive disease (PD), and not evaluable (NE). The corresponding 2-sided 97.5% exact CI for ORR will also be provided. Participants with only unknown or missing responses will be treated as non-responders, i.e., these participants will be included in the denominator when calculating percentages of response. A list of IRC-assessed response at each visit will be listed.

For subgroup analysis, ORR will be presented using forest plot for the following categories: Age, Sex, Ethnic Background, ISS Staging at Screening, Number of prior lines of therapy, Type of myeloma, , Refractory to prior anti-cancer therapy, Cytogenetics Risk as defined in Section 5.3.2

A waterfall plot showing the maximum percent reduction from baseline in Serum M-protein, or Urine M-protein, or difference between two types Serum FLC [Kappa light chain (Kappa LC) and Lambda light chain (Lambda LC)] for each subject will be produced using by dose level. The plot will be color-coded for M-protein types and Serum FLC, etc. Indication of the best overall response will be provided below the plot. Only the assessments from the start of treatment up to the start of new anti-cancer therapy will be considered. Only new systemic anti-cancer drugs taken are considered as anti-cancer therapy (radiotherapy and surgeries are not considered as systemic anti-cancer therapy for the purpose of this analysis).

The maximum percent reduction will be plotted in the following hierarchical order:

- [1] Plot Serum M-protein maximum percent reduction from baseline if data is available;
- [2] If [1] is not feasible, plot Urine M-protein maximum percent reduction from baseline if data is available;
- [3] If both [1] and [2] are not feasible, plot maximum percent reduction from baseline for difference between two types of Serum FLC if data is available;

Difference between two types of Serum FLC

The percent change from baseline for difference between two types of Serum FLC is defined as:

$$(\text{post-baseline difference} - \text{baseline difference}) / \text{baseline difference} * 100\%$$

To calculate the difference, the “involved” and “non-involved” light chains must be determined at first based on the ratio of non-missing values for Serum Kappa LC protein and Serum Lambda LC protein at baseline.

The detailed algorithm is provided as below:

- If the baseline ratio of (Kappa LC/Lambda LC) > 1.65, then Kappa LC is defined as involved FLC, and Lambda LC is defined as non-involved FLC. Then
 - Difference between involved and uninvolved = Kappa LC - Lambda LC
- If the baseline ratio of (kappa/lambda) < 0.26, then Lambda light chain is defined as involved FLC, and Kappa light chain is defined as non-involved FLC
 - Difference between involved and uninvolved = Lambda LC - Kappa LC
- If the baseline ratio of (Kappa LC/Lambda LC) ≤ 1.65 and ≥ 0.26 , then “involved” and “non-involved” FLC can not be determined (ratio is normal), and maximum percent reduction from baseline for difference between two types of Serum FLC won't be available.

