15.6.3. Efficacy

Laboratory Parameters
Serum M-protein, Urine M-protein, Serum FLC

 • If a laboratory value which is expected to have a numeric value for summary purposes, has a non-detectable level reported in the database, where the numeric value is missing, but typically a character value starting with '<x' or '>x' (or indicated as less than x or greater than x in the comment field) is present, the number of significant digits in the observed values will be used to determine how much to add or subtract in order to impute the corresponding numeric value. 
 ○ Example 1: 2 Significant Digits = '< x' becomes x – 0.01 ○ Example 2: 1 Significant Digit = '> x' becomes x + 0.1 • Example 3: 0 Significant Digits = '< x' becomes x – 1

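### The waterfall plot chooses its marker by data availability, not baseline measurability, so a trace serum or urine M-protein can displace the marker on which the participant is measurable

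*SAP*

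**What the plan says.** SAP Section 7.1.2 sets a three-step order for the waterfall bars. Step [1] is "Plot Serum M-protein maximum percent reduction from baseline if data is available". Step [2] is "If [1] is not feasible, plot Urine M-protein maximum percent reduction from baseline if data is available". Step [3] moves to the difference between involved and uninvolved serum FLC when neither earlier step is feasible. The section does not define 'feasible'. The bars are colour-coded by marker, and the best overall response is shown beneath them.

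The only marker-specific condition in that section is on FLC. With a normal baseline kappa/lambda ratio, the "maximum percent reduction from baseline for difference between two types of Serum FLC won't be available".

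Two other places bear on the rule:

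- Section 7.2.1.5, Table 4, footnote 1 states: "Adequate baseline assessment is defined as at baseline, a patient has at least one of the following measurements". It then lists serum M-protein of at least 0.5 g/dL, "Urine M-protein ≥ 200 mg/24h", or involved FLC of at least 10 mg/dL with an abnormal ratio. One marker is enough.
- Section 15.6.3 turns non-detectable serum, urine and FLC results into numbers: "the number of significant digits in the observed values will be used to determine how much to add or subtract".

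The display list (Section 15.13.7, Figure 2.0030, shell RE8b) has an empty programming note, so it adds no rule.

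**The concern.** Table 4 shows that the SAP expects some participants to be adequately measured on urine or FLC alone. The waterfall rule does not use that information. It asks only whether a value exists, and Section 15.6.3 makes values exist in some cases where the assay detected nothing. A participant followed on urine or FLC can then be drawn on a trace serum value whose percentage movement is mostly noise.

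What is at stake is the reading of the figure. A responder on the measurable marker may show no change or a rise, and a participant without any real change may appear to have a substantial fall. Either can contradict the response label under the bar.

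**Working it through.** The plan gives no figure to reproduce, so the check applies the rule to individual cases.

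**Formula.** Section 7.1.2 gives percent change for the FLC difference as (post-baseline − baseline) / baseline × 100. I assume the same form for serum and urine, for which none is written out.

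**Imputation under Section 15.6.3.** Serum '<0.10' becomes 0.10 − 0.01 = 0.09, which is non-zero, so a percent change can be computed. Serum '<0.1' becomes 0.1 − 0.1 = 0, so the percent change has a zero denominator.

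**Two rules compared.** The literal rule takes the first marker, in the order serum, urine, FLC, for which a percent change can be computed. The measurability rule takes the first marker in that order that also meets its Table 4 threshold.

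All participant values below are hypothetical. Serum is in g/dL, urine in mg/24h and FLC difference in mg/dL. Each post-baseline value is the lowest observed. The FLC ratio in cases 3 and 4 is taken as abnormal. Involved FLC is at least as large as the difference of 80, so it exceeds either FLC threshold in the SAP.

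| Case | Values, baseline to lowest | Literal rule | Measurability rule | Gap (points) |
|---|---|---|---|---|
| 1. Urine-only | serum 0.2 to 0.1; urine 1000 to 1000 | serum (0.1 − 0.2)/0.2 = −50% | urine 0% | 50 |
| 2. Urine-only | serum 0.1 to 0.2; urine 1000 to 100 | serum (0.2 − 0.1)/0.1 = +100% | urine (100 − 1000)/1000 = −90% | 190 |
| 3. FLC-only | serum '<0.10' (0.09) at both times; urine 0; FLC 80 to 8 | serum 0% | FLC (8 − 80)/80 = −90% | 90 |
| 4. FLC-only | serum 0; urine 50 to 50; FLC 80 to 8 | urine 0% | FLC −90% | 90 |
| 5. Urine-measurable | serum missing or 0; urine 1000 to 100 | urine −90% | urine −90% | 0 |
| 6. Serum-measurable | serum 2 to 0.5 | serum (0.5 − 2)/2 = −75% | serum −75% | 0 |

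Cases 1 to 3 show step [1] taking a sub-threshold serum value. Case 4 shows the same fault at step [2]. Cases 5 and 6 show where the two rules agree: serum is measurable, or serum is missing or zero and the next usable marker is the measurable one.

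**The case against.** The strongest reply is that steps [2] and [3] are triggered by the earlier step being not feasible, which is wider than data being missing. A percent change with a zero denominator is the natural example. So a baseline that is missing, zero, or '<0.1' imputed to 0 moves on to the next marker, and the hierarchy works. This stands. It also rules out two inferences a reader might draw: that a participant with light-chain-only disease can never reach the FLC step, and that everyone below 0.5 g/dL serum is affected. The SAP does not say how an absent M-protein is recorded, and Section 15.6.3 covers only results with a stated limit.

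Further points against, and what remains of each:

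- The plot shows the largest reduction. The +100% bar in case 2 therefore needs every post-baseline serum value to be at least 0.2 g/dL; one return to 0.1 would give 0%. That is correct, but cases 1, 3 and 4 do not depend on it, and a 0% bar would still conflict with −90% on urine.
- Colour-coding and the printed response let a reader notice a mismatch. That is partly true: the colour shows which marker was used, not whether it was measurable.
- The printed response need not be the IRC's. Section 7.1.2 names no assessor; the IRC is inferred from its place under the primary endpoint. The possible mismatch does not depend on which assessor it is.
- Figure 2.0030 is tagged for the headline results and the primary analysis, not the end-of-study package, and this version describes some primary-analysis work in the past tense (Sections 9 and 12.2). So a change would alter no listed end-of-study output. This limits the practical gain but does not correct the rule.

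**Conclusion.** The point holds as a minor defect in one descriptive figure. Read literally, Section 7.1.2 gives a misleading bar for a participant whose serum or urine baseline is non-zero, or imputed as non-zero, but below the Table 4 threshold, and who is measurable only on a marker later in the order. In the assumed examples the gap is 50 to 190 percentage points, with a change of sign in one.

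The number of such participants cannot be derived from the document. A reader might take the share below the serum threshold as the share affected. If that share were 10% to 30% (an assumption), it would give 10 to 30 bars per 100, but only as an upper bound: participants who fall through to their measurable marker are included in it and are plotted correctly.

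Nor does the point reach the primary result. ORR, its two-sided 97.5% exact CI and the test against 15% use confirmed response and do not depend on the marker chosen for this plot.

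**What to change.** In Section 7.1.2, steps [1] to [3]:

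- Keep the order serum, urine, FLC, but plot the first marker that meets the SAP's adequate-baseline threshold: serum at least 0.5 g/dL, urine at least 200 mg/24h, or involved FLC above its threshold with an abnormal ratio.
- First reconcile the FLC threshold, which is 10 mg/dL in Table 4 and 5 mg/dL in the note to Table 5. The revision list in Section 1.1 records only the Table 4 value as updated.
- Define 'not feasible' as not measurable at baseline, or percent change not computable. This also settles the zero-baseline case.
- Flag or footnote participants who meet none of the thresholds, because the section promises a bar for each subject.

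The cost is a few lines of SAP text and one condition in the program for Figure 2.0030. The small downside is that participants below all three thresholds would have a flagged bar or none. If the figure is not rerun, a footnote saying that the marker was chosen by availability would tell the reader what is needed.
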